6.5.1.2 Assessment of adverse events

All AEs must be elicited, documented and reported by the investigator to the sponsor from the time that a study subject signs the IC form until the end-of-study visit (14-25 days after the last study treatment administration).

SAEs and other significant AEs should be followed up until resolved or until the event is considered a chronic or stable outcome, or both.

An AE may be notified to the investigator by the study subject (or his/her caregiver) or observed by the investigator clinically, or be an adverse change in laboratory assessment results. The investigator will evaluate the subject's AEs at each visit by asking a standard question such as "Since you were last asked, have you felt unwell or different from the usual in any way?"

The investigator will assess and record the causality and severity of the AEs. Causality should be assessed in relation to the investigational medicinal product (see criteria for causality and severity below).

Causality criteria:

Related: The temporal relationship of the AE/SAE onset to the administration of the investigational medicinal product makes a causal relationship possible, and other drugs, therapeutic interventions or underlying conditions do not provide a sufficient explanation for the AE/SAE.

Not related: The temporal relationship of the AE/SAE onset to the administration of the investigational medicinal product makes a causal relationship unlikely, or other drugs, therapeutic interventions or underlying conditions provide a sufficient explanation for the AE/SAE.

Severity criteria:

Mild: Discomfort noticed, but it does not affect normal activity.

Moderate: Discomfort sufficient to reduce or affect normal daily activity.

Severe: Incapacitating with inability to work or perform normal daily activity.

From the time that a study subject candidate signs the IC form, newly appearing diagnosed diseases will be recorded on the AE CRF.

Investigators must report all AEs to the sponsor on a specific AE CRF irrespective of their assessment of the causal relationship of the investigational medicinal product to the event.

6.5.1.3 Reporting of serious adverse events by the investigator

The investigator must report all SAEs within 24 hours of becoming aware of an SAE. SAEs must be reported within 24 hours regardless of the time that may have elapsed since the time the event occurred and regardless of the causal relationship of investigational medicinal product to the event.

DNO 090017ff823c9bac / 1.0 Approved 38 / 58

In this study, the following events will not be reported as SAEs:

- hospitalisation and elective surgery for treatment of pre-existing condition that has not exacerbated during the study
- hospitalisation for procedures and/or evaluations in connection with ALS such as evaluation for the need or initiation of ventilatory support (e.g. NIV) or gastrostomy.

All SAEs should be reported electronically by the investigator or other relevant study centre personnel and submitted by the investigator. Optionally, if the investigator is not able to submit the SAE electronically, a paper version of the SAE form can be completed and sent by e-mail or fax. The SAE reporting contact information can be found on the SAE form and will be filed in the investigator's study file.

If the initial report is reported by phone or e-mail to the study monitor or other contract research organisation (CRO) personnel and the study centre personnel are unable to fill in the SAE electronically within 24 hours, a paper SAE form will be initiated by the person receiving the report. The investigator must report the SAE electronically as soon as possible.

The minimum criteria for SAE reporting are: the event or outcome meets the SAE definition, the event happens to an identifiable study subject, and the event is reported by an identifiable and qualified reporter (usually an investigator or other qualified study centre personnel)

A follow-up report to an SAE should be prepared if any relevant change in the condition of the study subject occurs after the initial report. The follow-up report should be documented as an update to the initial report.

SAEs that occur after the end-of-study visit (14-25 days after the last study treatment administration), should be reported if the investigator feels that there is a reasonable possibility for the event to have been caused by the study subject's participation in the study.

6.5.1.4 Reporting of serious adverse events to competent authorities and ethics committees

The sponsor is responsible for expediting all suspected unexpected serious adverse reactions (SUSARs) as well as other safety issues requiring expedited reporting to the relevant authorities within applicable timelines. These tasks can also be carried out by a delegate of the responsible sponsor.

Notification of the ethics committees (ECs) and institutional review boards (IRBs) about all relevant events (SUSARs, other relevant safety information) will be performed by the sponsor or delegate of the responsible sponsor and/or by the investigator according to applicable regulations.

The Sponsor will inform all investigational sites about suspected unexpected serious adverse reactions (SUSARs) as well as other safety issues according to all applicable regulations.

The expectedness evaluation is required for regulatory reporting and it is performed by the sponsor. The expectedness in this study is evaluated against the Reference safety information section in the current ODM-109: oral levosimendan capsule for treatment of ALS investigator's brochure.

DNO 090017ff823c9bac / 1.0 Approved 39 / 58

6.5.2 Special situations

Special situations with study treatment are defined as:

- medication error
- overdose
- abuse
- misuse
- interaction

These special situations with study treatment are reported on the Special situations with study treatment CRF even if there is no accompanying AE. All clinical manifestations in relation to these special situations will be reported as AEs or SAEs at the same time using the corresponding section of the CRF.

6.5.3 Pregnancy during the study

Whenever it becomes known that a study subject or a partner of a study subject was pregnant during the exposure to study treatments, the outcome of the pregnancy, delivery, postpartum recovery and the clinical condition of the offspring during the neonatal period should be reported, subject to the study subject's or the partner's consent. A pregnancy follow-up form will be provided to the investigator for completion after the sponsor has received the initial report.

Any case of pregnancy during a clinical study should be reported by the investigator in the same way as an SAE.

6.5.4 Clinical safety assessments

Vital signs (HR, systolic and diastolic BP) and standard 12-lead ECG will be assessed at screening, at each visit during the treatment period before and 30-90 minutes after the morning dose of the study drug, and at the end-of-study visit. At baseline visit, vital signs and ECG will be assessed before and 45-120 minutes after the morning dose of the study drug.

At the screening visit, only supine HR and BP will be measured. At baseline visit, each visit during the treatment period and end-of-study visit, supine HR and BP will be assessed after a 5-minute rest. Subjects will then be asked to stand up and after 3 minutes, standing HR and BP will be measured (orthostatic test). In case the subject is not able to stand, only supine HR and BP will be measured.

A standard 12-lead ECG (central reading) will be recorded with subject lying supine and after a 5-minute rest. 3 baseline recordings of ECG in 1-3 minutes intervals will be done before dosing at visit 1 (baseline). The HR, RR, PR and QT intervals and QRS duration will be analysed in the central ECG laboratory. QTc will be calculated using both Bazett's and Fridericia's correction. Each ECG will be assessed as normal/abnormal by the central ECG laboratory. Clinical significance of the abnormalities will be assessed by the investigator.

DNO 090017ff823c9bac / 1.0 Approved 40 / 58

Additional 1-2 assessments of 12-lead ECG should be performed within 5-10 minutes from each other (all before the morning dose), if the HR in the first recording was increased from baseline (visit 1) as follows:

- > 20 bpm if the subject is receiving the study treatment 1 mg b.i.d., to assess the need for dose reduction (see section 5.3.2)
- > 30 bpm if the subject is receiving the study treatment 1 mg once daily, to assess the need for discontinuation (see section 4.5)

If the HR increase is not repeated in the second ECG, no further ECG recordings are needed.

Physical examination will be performed at screening and the end-of-study visit. Weight will be measured at screening, at visits 1, 3, 4, 5, 6, 7, 8 and at the end-of-study visit. Height will be recorded at screening only.

In case there are abnormal findings, control assessments can be performed according to the judgement of the investigator.

6.5.5 Assessment of suicidality

Suicidality will be assessed by asking the following standard questions at screening, at each visit during the treatment period before dosing, and at the end-of-study visit:

Screening:

- 1. During the past 3 months, have you wished you were not alive anymore or had any thoughts about ending your life?
- 2. During the past 3 months, have you done anything or prepared to do anything to end your life?

Treatment period and end-of-study:

- 1. Since the last visit, have you wished you were not alive anymore or had any thoughts about ending your life?
- 2. Since the last visit, have you done anything or prepared to do anything to end your life?

The second question (2) will be asked only in cases where the answer to the first question (1) has been 'yes'.

6.5.6 Laboratory safety assessments

The following laboratory tests will be taken at the screening visit after at least 10 hours of fasting:

Haematology:

- Haemoglobin
- Haematocrit
- Erythrocyte count
- Leukocyte count
- Platelet count
- Differential count (lymphocytes, monocytes, eosinophils, neutrophils, basophiles)
- Mean corpuscular volume

Mean corpuscular haemoglobin

Chemistry:

- Albumin
- Alkaline phosphatase (ALP)
- Bilirubin total
- Bilirubin conjugated
- Calcium
- Creatine kinase
- Creatinine
- Creatinine clearance
- C-reactive protein
- Gamma-glutamyl transferase (GGT)
- Alanine aminotransferase (ALT)
- Aspartate aminotransferase (AST)
- Glucose
- Lactate dehydrogenase
- Potassium
- Sodium
- Troponin T
- TSH

Urinalysis:

- Glucose
- Protein
- Erythrocytes
- Leucocytes

Serology:

- Hepatitis B surface antigen (HBsAg)
- Hepatitis C virus antibody (HCVAb)

Haematology, chemistry (except TSH) and urinalysis will be repeated at each visit during the treatment period and at the end-of-study visit.

A pregnancy test for female subjects of childbearing potential will be performed at screening and baseline and at each visit during the treatment period (except visit 2, i.e. 2 weeks after baseline) and at the end-of-study visit.

The investigator will review all laboratory results and assess them for clinical significance. In case there are abnormal findings, control assessments can be performed according to the judgement of the investigator.

Instructions for the collection, handling, storage and transportation of samples will be provided before the start of the study.

6.6 Changes implemented due to COVID-19 pandemic

In case visits 7 (Week 36), 8 (Week 48) and/or end-of-study visit (14-25 days after visit 8) described in Table 1 and in sections 6.1.2 and 6.1.5 cannot be conducted at the study centre

DNO 090017ff823c9bac / 1.0 Approved 42 / 58

within the visit window due to restrictions related to COVID-19, a telephone visit (could also be a home visit or video call) should be arranged.

The telephone visit should include all protocol assessments that can be performed remotely (see table below) and should take place within the original visit window. The decision to replace the study centre visit with a telephone contact will be made by the investigator case by case, and the sponsor should be informed of each case as early as possible.

In addition to the telephone visit, the investigator should make reasonable efforts to obtain 12-lead ECG, laboratory safety assessments and vital signs for each visit. These measurements may include local practitioners and resources. In case these assessments, at least vital signs, cannot be obtained within a reasonable time after the visit 7 telephone contact, the benefit-risk ratio for the subject to continue in the study should be reassessed.

Visit 8 telephone contact should take place at the time of stopping study medication. All safety data which are possible to obtain locally should be collected prior (on treatment) or at the remote visit: the study treatment should be stopped at the time of the remote visit.

The following assessments will not be performed at telephone visits: SVC supine, weight, sitting or orthostatic changes in vital signs, blood sampling for levosimendan, OR-1855 and OR-1896 PK, for riluzole concentration and for exploratory biomarkers, and physical examination.

All arrangements described in this section apply only to the extent that protocol requirements cannot be met because of COVID-19 restrictions. Study centre visits should take place to the extent possible and usual protocol requirements adopted for all subjects as soon as COVID-19 limitations permit.

Exceptional measures taken in response to COVID-19 and their impact on study results, such as tests done in a local laboratory, will be explained, assessed and reported in the clinical study report following ICH E3.

DNO 090017ff823c9bac / 1.0 Approved 43 / 58

Procedures at remote visits

Time	Visit 7 Week 36	Visit 8 Week 48	End-of- study
HR and BP	\mathbf{x}^1	\mathbf{x}^1	\mathbf{x}^1
12-lead ECG	\mathbf{x}^2	\mathbf{x}^2	\mathbf{x}^2
Laboratory safety assessments ³			
Haematology	X	X	X
Chemistry	X	X	X
Urinalysis	X	X	X
Pregnancy test for females of childbearing potential	x^4	\mathbf{x}^4	x^4
Study treatment	X	X	
ALSFRS-R	X	X	
CGI	X	X	
Borg CR10 scale	X	X	X
ESS	X	X	
PSQI	X	X	
Use of health care and home care resources use and non-medical assistive devices	X	X	
Assessment of suicidality	X	X	X
Status for NIV support, invasive mechanical ventilation by intubation or tracheostomy and survival	X	X	X
AEs and SAEs	X	X	X
Medical history and current medical conditions	X	X	X
Concomitant treatments	X	X	X

¹ Only in supine position after at least 5 min rest before the morning dose of the study treatment. The assessment should preferably be done by a health care professional. The use of alternative methods, including home devices are subject to sponsor approval.

7. DATA COLLECTION AND MANAGEMENT

The investigators and study centre personnel will prepare and maintain accurate source data for each study subject about clinical findings specified in the protocol. Source data include patient records, laboratory results and questionnaires if not collected electronically. The data from source documents will be recorded into an electronic data capture (EDC) system, Medidata Rave (Medidata Inc), using eCRFs at the study centre. Safety laboratory, spirometry and ECG will be analysed centrally and results will be uploaded to the Rave system and electronically signed by the investigator. All data on the eCRFs must be verifiable in the source data or patient records unless eCRF data are declared as source data.

² The measurement should be taken using the local ECG device, preferably before the morning dose of the study treatment, after at least 5 min rest. A copy of the trace (paper or electronic) should be provided.

³ Standard biochemical, electrolyte and haematological test panels of the local laboratory will be accepted. A copy of the laboratory report with local reference range should be provided.

⁴ Test kits for urine pregnancy test should be provided to the subject for testing at home (unless taken in a local laboratory).

Investigators and other relevant study centre personnel will be trained to use the eCRFs. After completion of training, they are provided with user names and authorised access to enter and correct data on the eCRFs.

Electronic queries about missing, misleading, incomplete or illogical data will appear in the EDC system. An audit trail within the system will track all changes/corrections made. The investigator has to confirm the content of the eCRF with an electronic signature.

Individual data fields in the EDC system may be locked on an ongoing basis during the study. The fields may be unlocked if further updates are needed. When all data have been entered and all queries resolved, the whole database will be locked. Only authorised and well-documented updates to the study data are possible after the database lock.

Further details regarding data collection and management are presented in the data management plan.

8. STATISTICAL METHODS

8.1 Statistical hypotheses

The main statistical hypothesis of the study is to show the superiority of levosimendan against matching placebo in SVC (supine) at 12 weeks. The statistical hypothesis will be two-sided comparing change from baseline to 12 week pre-dose sample using the mixed model for repeated measures (MMRM) at a nominal 5% significance level.

H0: $\Delta SVC\%_{levosimendan} = \Delta SVC\%_{placebo}$

H1: $\Delta SVC\%$ levosimendan $\neq \Delta SVC\%$ placebo

8.2 Estimation of sample size

Sample size estimation is primarily based on the study 3119001 LEVALS SVC (supine) results (Table 6). The LEVALS study had placebo controlled data only up to 2 weeks and therefore extrapolation of the results is needed. The placebo effect from phase II tirasemtiv trial BENEFIT-ALS (Shefner JM et al., 2016) is also evaluated.

Assuming at least 3.6% difference between treatment arms and common standard deviation of 10%, 164 evaluable subjects have 90% power to detect a statistically significant difference at two-sided 5% level using 1:1 allocation ratio and two group T-test. Randomisation of 450 subjects to study using a 2:1 allocation ratio (approximately 300 levosimendan and 150 placebo treated subjects) allows approximately 20% drop out rate.

Based on dexpramipexole phase III study EMPOWER (Cudkowicz ME et al., 2013) 12 point reduction in total ALSFRS-R score and a 15% mortality rate at 12 months can be assumed in placebo treated patients. Assuming 10 point decline, with 8 point standard deviation, in ALSFRS-R and 20% relative improvement in survival 450 patients provide approximately 80% simulated power to detect statistically significant difference using joint rank test. With 450 subjects and assuming 48 week levosimendan event rate of 73% and hazard ratio of 0.70, time to respiratory event has approximately 70% power to detect statistically significant difference using log-rank test.

Table 6.	Mean ((SD)	change fi	rom base	line	SVC ((supine)

Treatment	2 weeks	12 weeks
Levosimendan 1 mg x 2	+2.4 (8.3)	-4.9
Levosimendan 1 mg x 1	+0.8 (8.6)	
Placebo	-3.6 (9.4)	-17.7 ¹
Placebo (BENEFIT-ALS)	-1.4	-8.5

¹ Extrapolated from the data

8.3 Analysis populations

Intent-to-treat (ITT) dataset, including all randomised subjects, will be used for the primary evaluation. Sensitivity analyses using full analysis set (FAS) and per-protocol (PP) dataset will be performed and described in the SAP. FAS includes all treated subjects with at least one post baseline SVC measurement. PP dataset includes all randomised subjects excluding subjects with relevant major protocol deviations. All subjects who received any study treatment will be included in the evaluation of safety. Subject classification will be completed during the blind review before the database lock and opening the treatment code.

8.4 Statistical analyses

Statistical analyses will be described in more detail in the SAP.

8.4.1 Demographic and other baseline characteristics

All relevant demographic and baseline characteristics will be summarised using descriptive statistics. The number and reasons for discontinuations will be listed and tabulated by treatment groups.

An authorised person will code medical history and concomitant diseases using standard coding dictionaries.

8.4.2 Treatment compliance and extent of exposure

The number of exposed subjects, the number of dispensed and returned study treatments and the duration of study treatment exposure will be tabulated with descriptive statistics.

8.4.3 Analysis of efficacy

The primary efficacy variable SVC (supine) will be compared between the treatment arms using the MMRM with between subject effects for treatment, centre and randomisation strata, time as within subject effect, and baseline value (visit 1) as a covariate. Primary efficacy will be evaluated at 12 weeks using contrasts to obtain estimates from the primary model including all SVC measurements prior to 12 weeks. Any missing data will be imputed using multiple imputation method. Effect of missing data imputation will be evaluated analysing observed data only and estimating the slope of decline using the random slope model. Several sensitivity subgroup analyses will be performed and defined in the SAP. Additional evaluations will be performed including all data through 48 weeks, using the MMRM.

DNO 090017ff823c9bac / 1.0 Approved 46 / 58

SD = standard deviation

Secondary efficacy endpoints will be tested in following hierarchy to preserve the overall alpha level:

- 1. Combined assessment of ALSFRS-R function and survival through 48 weeks
- 2. Time to respiratory event through 48 weeks
- 3. CGI through 48 weeks
- 4. Supine Borg CR 10 scale at 12 weeks
- 5. Slope of decline in respiratory function of ALSFRS-R through 48 weeks

The efficacy variables time to respiratory event, time to NIV or death, time to SVC (supine) decline of 20%, time to SVC (supine) \leq 50% of predicted, time to ALSFRS-R total score decline of 20% and time to decline in ALSFRS-R respiratory domain will be evaluated using the Cox's proportional regression model. The model will include effect for treatment and will be adjusted for randomisation strata. Premature discontinuations will be censored from the analyses. Censoring rules will be defined in the SAP.

The efficacy variables ALSFRS-R total score and its subdomain scores will be performed through 48 weeks. Primary analysis will combine change from baseline to 48 weeks and survival through 48 weeks in joint rank analysis (Berry JD et al., 2013) using Wilcoxon-Mann-Whitney test. Slope of decline will be estimated using the random slope model. Additional analyses will be conducted using the MMRM and estimates for individual time points will be done using contrasts. Imputation of missing data using the multiple imputation method will be considered.

CGI, Borg CR10 (sitting, supine and orthostatic changes), ESS and PSQI will be evaluated using the MMRM and estimates for individual time points will be done using contrasts. In addition categorical analyses for ESS and PSQI will be performed using repeated measures logistic regression using the generalised estimating equation (GEE) approach.

All efficacy data will be listed and summarised over the time and by treatment groups using appropriate descriptive statistics. Health and home care resource use data will be summarised in the study report, but any further analysis for potential pharmacoeconomic purposes will be reported separately.

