DSMB Data and safety monitoring board

EBV Epstein-Barr virus

EC Ethics committee

ECG Electrocardiogram

eCRF Electronic case report form

EDC Electronic data capture

EMG Electromyogram

ESS Epworth Sleepiness Scale

FAS Full analysis set

FDA U.S. Food and Drug Administration

GCP Good clinical practice

GGT Gamma-glutamyl transferase

GMP Good manufacturing practice

HADS Hospital Anxiety and Depression Scale

HAV Hepatitis-A virus

HBc Hepatitis B virus core antigen

HBsAg Hepatitis B surface antigen

HCV Hepatitis C virus

HCVAb Hepatitis C virus antibody

HEV Hepatitis-E virus

HF Heart failure

HIV Human immunodeficiency virus

HR Heart rate

IC Informed consent

ICD Implantable cardioverter defibrillator

INR International normalised ratio

IRB Institutional review board

ITT Intent-to-treat

i.v. Intravenous

IWRS Interactive web response system

LC-MS/MS Liquid-chromatography-tandem mass spectrometry

MedDRA Medical Dictionary for Regulatory Activities

MG Myasthenia gravis

MHRA The Medicines and Healthcare Products Regulatory Agency

MMRM Mixed model for repeated measures

NIV Non-invasive mask ventilation

PD Pharmacodynamic(s)

PG Pharmacogenomic(s)

PK Pharmacokinetic(s)

PP Per-protocol

QTcF QTc Fridericia

SAE Serious adverse event

SAP Statistical analysis plan

SBP Systolic blood pressure

SNP Sniff nasal pressure

SVC Slow vital capacity

t_{1/2} Terminal elimination half-life

TdP Torsades de Pointes

TIA Transient ischemic attack

TSH Thyroid-stimulating hormone

VAS Visual analogue scale

ULN Upper limit of normal

Note on usage of terms:

Orion Corporation Orion Pharma is hereafter in this document called "Orion" or sponsor.

The term 'investigator' in the text of the protocol refers to the principal investigator or co-investigator.

1. Introduction

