4.5 Removal of subjects from treatment or assessment

Study subjects are free to discontinue the study at any time without providing a reason. However, the investigator should try to identify the reason and document it in the CRF.

A subject must discontinue the study treatment for the following reasons:

- HR increase of > 30 bpm from baseline (visit 1) at the dose level of 1 mg once daily in 3 separate ECG recordings, taken within 5-10 minutes from each other before the morning dose of the study drug (see also section 6.5.4).
- Life-threatening supraventricular or ventricular arrhythmia.
- The investigator judges that it is in the best interest of the subject to stop the study treatment due to any other abnormality compromising patient safety. However, the investigator should consult the medical monitor whenever possible in these instances.
- Pregnancy.
- Invasive mechanical ventilation by intubation or tracheostomy.

The subjects who have discontinued the study medication, but continue in the study, are encouraged to follow the study visit and phone call schedule according to the study protocol for recording ALSFRS-R, ventilatory support and survival status. End-of-study visit assessments for these subjects will be performed 14-25 d after the last study treatment administration.

A subject must discontinue the study if the investigator or the sponsor considers the discontinuation to be medically necessary or in the best interest of the subject.

Irrespective of the reason for discontinuation, the subject should be invited to end-of-study assessments as soon as possible. As long as the subject consents, all relevant assessments, at least those of safety, should be performed, preferably according to the schedule for the end-of-study assessments.

The study monitor should be notified about premature discontinuations by email/phone/fax within 24 hours in the event of discontinuation due to an SAE (see section 6.5.1.3) or within 7 days in the event of discontinuation due to another reason.

DNO 090017ff823c9bac / 1.0 Approved 22 / 58

Subjects who prematurely discontinue will not be replaced. Discontinued subjects are not allowed to re-enter the study.

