6.2.9 Other assessments

Subject's status for NIV support, invasive mechanical ventilation by intubation or tracheostomy and survival will be recorded at all visits.

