Tipping point analyses will be considered for further evaluating sensitivity of the results with respect to missing data. In such an analysis, the distribution of missing data in the active treatment group would be shifted by varying amounts, until a point is found where the results of the analysis cross the threshold of statistical significance specified in section 6.2.2. The plausibility of a shift of the found size is then used to assess the robustness of results to unobserved differences due to missing data.

Subjects who discontinue study treatment but remain in the study can continue to contribute ALSFRS-R data, which will be included in the analyses where applicable. However, in time-to-

event analyses subjects will be censored from follow-up one day after study treatment discontinuation.

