7.5.2.3 Respiratory event and other time-to-event endpoints

A 'time to respiratory event' composite endpoint consists of the following events:

- A decrease of one or more points from baseline in any of the ALSFRS-R respiratory function subdomain scores (items 10–12).
- Starting non-invasive mask ventilation (NIV).
- Meeting 'protocolised' criteria for NIV: SVC (supine) $\leq 50\%$ predicted.
- Invasive mechanical ventilation by intubation.
- Invasive mechanical ventilation by tracheostomy.
- Death.

Time to respiratory event is reached whenever any of the criteria has first been met.

The following time-to-event secondary efficacy variables will be evaluated using Cox's proportional hazards regression:

1. Time to tracheostomy, continuous ventilator dependence, or death (TRCVDDTH)
2. Time to NIV or death (NIVDEATH)
3. Time to respiratory event (RESPEVNT)

Individual components of all the composite endpoints will be analysed in the same fashion:

1. Time to continuous ventilator dependence (ALSFRS-R item 12 ≤ 1 ; CVD)
2. Time to decline from baseline in any ALSFRS-R respiratory domain score (FRSBR1D)
3. Time to SVC (supine) $\leq 50\%$ of predicted (SVC50PP)
4. Time to non-invasive mask ventilation (NIV)
5. Time to intubation (INTUB)
6. Time to tracheostomy (TRACH)
7. Time to death (DEATH)

As will these additional endpoints derived from the SVC and ALSFRS-R values:

1. Time to decline from baseline SVC (supine) by $\geq 20\%$ (SVC20PD)
2. Time to decline from baseline ALSFRS-R total score by $\geq 20\%$ (FRS20PD)
3. Time to continuous use of NIV during the night (ALSFRS-R item 12 ≤ 2)

The data for the time-to-event variables will be stored in the ADTTE dataset with parameter names corresponding to those in parentheses above.

The analysis model will include an effect for treatment, and will be adjusted for randomization strata. Premature discontinuations will be treated as right-censored in the analyses. Censoring rules for different scenarios are described in **Error! Reference source not found..** For the purpose of determining the end date, survival and ventilation status are considered to be assessed daily; ALSFRS-R and SVC measurements are assessed only on study visits. For composite

endpoints, the date of last assessment is defined to be the latest date at which the endpoint can be fully assessed: that is, the earliest date in the set of latest assessments of each of its component endpoints.

Table 2. Censoring rules for time-to-event analyses.

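### Time to NIV or death does not count intubation or tracheostomy, so a subject ventilated invasively without earlier NIV is censored because of respiratory failure

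*Protocol*

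**What the plan says.** **Definition.** Protocol 8.4.3 lists the endpoint for Cox regression: "The efficacy variables time to respiratory event, time to NIV or death, time to SVC (supine) decline of 20" per cent, followed by further endpoints. SAP 7.5.2.3 lists it as "Time to NIV or death (NIVDEATH". Neither document adds a component. The protocol's abbreviation list reads "NIV Non-invasive mask ventilation", so the term does not extend to invasive ventilation. SAP 7.5.2.3 confirms this by giving invasive ventilation its own parameters, "Time to intubation (INTUB" and "Time to tracheostomy (TRACH".

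**Stopping treatment.** Protocol 4.5 includes "Invasive mechanical ventilation by intubation or tracheostomy" among the reasons for which study treatment must end.

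**Censoring.** SAP 6.2.5 says that in time-to-"event analyses subjects will be censored from follow-up one day after study treatment discontinuation". Table 2 in SAP 7.5.2.3 repeats this, with the last endpoint assessment as the end date. A separate row of that table counts death as an event, dated at death, when death is part of the endpoint.

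**Status and data.** SAP 7.5.2 treats endpoints outside the testing hierarchy as supportive, and NIVDEATH is outside it. Protocol 6.2.9 states: "Subject's status for NIV support, invasive mechanical ventilation by intubation or tracheostomy and survival will be recorded at all visits".

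**The concern.** Invasive ventilation is a more severe form of respiratory failure than the start of mask ventilation. One would expect an endpoint built from NIV and death to count it, or the plan to say why it does not. Here it is not counted, and the rule on stopping treatment then removes the subject from the risk set at that moment. A Cox model assumes that a censored subject has the same later risk as comparable subjects still followed. That is doubtful for someone censored because of intubation or tracheostomy.

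What is at stake is the interpretation of one named efficacy variable: its Kaplan-Meier curves, and its hazard ratio as a summary of ventilatory failure or death.

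**Working it through.** The plan gives no event rate, hazard ratio or power for this endpoint, so there is no figure to reproduce. The check traces the rules for one subject and then asks what arithmetic can and cannot show.

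**Tracing a subject intubated or tracheostomised with no earlier NIV**

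1. *Is there a NIVDEATH event on that day?* No. The components are NIV and death (protocol 8.4.3, SAP 7.5.2.3).
2. *Does treatment continue?* No. Protocol 4.5 requires it to stop.
3. *Does follow-up for the endpoint continue?* Under SAP 6.2.5, for one more day. SAP 7.5.2.3 treats ventilation and survival status as assessed daily, so the end date falls at about the treatment stop.
4. *Would a later death count?* Under the text of SAP 6.2.5, not if it comes more than one day after the stop. Under the death row of Table 2, it might. The table does not rank its rows.
5. *Does imputation recover the event?* No. The list of analyses with multiple imputation in SAP 6.2.5 includes time to respiratory event but not NIVDEATH.
6. *Is the event seen elsewhere?* Yes. It is a component of time to respiratory event, second in the hierarchy, and is analysed singly as INTUB or TRACH. Tracheostomy is also in the composite TRCVDDTH, which does not name intubation.

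Under either reading of step 4, no event is counted when invasive ventilation starts.

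**What arithmetic can show**

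The following rates are assumptions; none is in the documents. Take 40% with NIV or death by Week 48 in both arms (no treatment effect), and direct invasive ventilation of 2% or 6%. With exponential times and independent causes, the cumulative hazard over 48 weeks is −ln(1 − p):

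- NIV or death: −ln(0.60) = 0.511
- direct invasive ventilation: −ln(0.98) = 0.020 and −ln(0.94) = 0.062

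The hazard ratio (levosimendan/placebo) as written is 0.511/0.511 = 1.00 in every case. With invasive ventilation counted it is:

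- placebo 6%, levosimendan 2%: (0.511 + 0.020)/(0.511 + 0.062) = 0.531/0.573 = 0.93
- placebo 2%, levosimendan 6%: 0.573/0.531 = 1.08
- 2% in both arms: 0.531/0.531 = 1.00

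A simulation under the same assumptions (300:150 subjects, 20% dropout, 300 trials per case, Cox model with treatment only) agrees:

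| Direct invasive ventilation, placebo / levosimendan | Mean HR as written | Mean HR, broader endpoint | Events as written | Events, broader | Not counted |
|---|---|---|---|---|---|
| 6% / 2% | 1.009 | 0.933 | 161 | 171 | 10/171 = 5.8% |
| 2% / 6% | 1.011 | 1.086 | 160 | 174 | 14/174 = 8.0% |
| 2% / 2% | 1.02 | 1.02 | 162 | 168 | 6/168 = 3.6% |

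The as-written analysis returns about 1.0, the true value for NIV or death under these assumptions. The figures 0.93 and 1.09 are the hazard ratios of a broader endpoint. Because the causes were made independent, the calculation cannot measure bias from informative censoring. That bias depends on how strongly direct invasive ventilation predicts the NIV or death that would have followed, and the documents do not allow it to be estimated.

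**The case against.** The strongest reply is that NIV or death is a legitimate endpoint in its own right. The SAP has three composites with different components, and composites need not match. Intubation and tracheostomy are fully counted in time to respiratory event and in their own analyses. NIVDEATH is supportive, so no test in the hierarchy depends on it. The loss of follow-up comes from the general rule on treatment discontinuation, not from the endpoint's name.

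The group affected is also likely to be small. Protocol 1.1 describes NIV as common practice in later-stage patients, and entry requires sitting SVC of 60–90% of predicted with no assisted ventilation at screening or in the preceding 3 months.

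Most of this stands. It limits the importance of the point and rules out two stronger readings. A reader might infer that the NIVDEATH hazard ratio is wrong whenever direct invasive ventilation differs by arm. The calculation does not show that; it shows that a different endpoint has a different ratio. A reader might also infer that harm is hidden. An excess of invasive ventilation on levosimendan would still be counted in INTUB, TRACH and time to respiratory event.

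What the reply does not answer is that the definition and the censoring rule act together. The subject is not merely left without an event but is removed from follow-up because of respiratory failure. The SAP neither explains this nor settles what happens to a later death.

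**Conclusion.** The point holds as a minor one. Time to NIV or death, as defined, right-censors a subject who goes directly to invasive ventilation, and the censoring is caused by respiratory failure. It is therefore potentially informative. The handling of a later death is ambiguous between SAP 6.2.5 and the rows of Table 2.

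The size is unknown. Under assumed rates of 2% to 6% for direct invasive ventilation, about 4% to 8% of the broader endpoint's events would go uncounted. These rates are illustrative, and nothing in the documents supports the upper one. With equal rates in the two arms the hazard ratio does not move.

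No alpha, power, sample size or primary conclusion is affected. The conclusion rests on the definitions and censoring rules alone, not on the assumed rates.

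**What to change.** In SAP 7.5.2.3, define NIVDEATH as the first of NIV start, intubation, tracheostomy or death, dated from the ventilation and survival records. Declare the change in SAP 7.11. State in Table 2 which row prevails when a subject stops treatment and later dies. Keep the two-component definition as a sensitivity analysis.

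The cost is small. Ventilation and survival status are already recorded at all visits, and INTUB, TRACH and DEATH are already derived, so only the endpoint derivation and some SAP text change. No new data are needed. The change can be made in the SAP without a protocol amendment, since protocol 8.4 and 8.4.3 leave analysis detail and censoring rules to the SAP. The one drawback is that the endpoint becomes slightly broader than its protocol name, which the sensitivity analysis and the 7.11 entry make transparent.
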